### 4.7 TRIAL QUESTIONNAIRES

During LENS, participants will be asked to complete regular questionnaires including the EQ-5D, VFQ-25 and a trial-specific follow-up questionnaire. The EQ-5D and VFQ-25 will first be completed by the participant during the Screening visit on paper; and then after 2 years and at the final assessment. The trial-specific questionnaire will first be completed by telephone 6 months after the randomisation visit and then every 6 months by telephone thereafter and at the end of the study as described below. Follow up by medical records will be available when participants cannot be contacted. EQ-5D and VFQ-25 will be completed by participants on paper. The RCC and CCO will support the LCC with the conduct of telephone interviews for questionnaires where necessary.

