Analysis of the economic data will be performed by intention to treat in accordance with a pre-specified economic analysis plan (to be completed before unblinding of the data). The mean difference in total service costs between treatment allocation groups will be estimated using generalised linear regression adjusted for minimisation and baseline covariates (e.g. baseline health status) as appropriate. Costs will be assessed against the primary outcome, and the incremental cost per progression of DR (or DR related intervention) averted will be estimated for fenofibrate versus placebo. In addition, participant responses to the EQ-5D, at baseline and follow-up, will be used to estimate QALYs for each participant. The mean difference in QALYs between the groups will be estimated using generalised linear regression, allowing the incremental cost-per QALY to be estimated for fenofibrate versus placebo based on data collected to 4 years.

If the use of fenofibrate is found to result in an increased cost to the health service at four years, for a modest reduction in progression and a QALY gain of insufficient size to justify the extra cost, modelling will be used to extrapolate costs and QALYs beyond the follow-up period of the trial. This will rely on the fitting of parametric survival curves to the observed progression data, to predict progression beyond four years. Further downstream treatment/monitoring costs (associated with progression), and visual acuity and quality of life outcomes of referable disease, will then be modelled using a combination of data collected within the trial and published data on expected outcomes of treatment. This will allow longer-term cost-effectiveness, in terms of the incremental cost per QALY gained, to be estimated for fenofibrate versus placebo. The robustness of any

model based estimates of cost-effectiveness will be assessed using deterministic and probabilistic sensitivity analysis.

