4.4.3 Health economic assessments

Health economic assessments will be conducted to help guide the appropriate use of fenofibrate by health care providers. The detailed analysis plan for health economic assessments will be described in a separate document.

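### The protocol names baseline covariates for the cost regression but none for the QALY regression, although baseline EQ-5D is itself part of each QALY

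*Protocol*

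**What the plan says.** Protocol 6.2.2 specifies two regressions in one paragraph. The difference in total cost is to come from "generalised linear regression adjusted for minimisation and baseline covariates (e.g. baseline health status) as appropriate". Later in the paragraph, "participant responses to the EQ-5D, at baseline and follow-up, will be used to estimate QALYs for each participant", and then "The mean difference in QALYs between the groups will be estimated using generalised linear regression". No covariate is attached to that second model.

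Protocol 4.7 gives the EQ-5D schedule: the questionnaire "will first be completed by the participant during the Screening visit on paper; and then after 2 years and at the final assessment". The minimisation factors in Protocol 4.5.8 and SAP Appendix A do not include EQ-5D.

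Both documents leave the detail of the economic analysis to another place. Protocol 6.2.2 puts it under an economic analysis plan due before unblinding. SAP 4.4.3 says: "The detailed analysis plan for health economic assessments will be described in a separate document". SAP 7.1 adjusts the EQ-5D index for its baseline value and the minimisation criteria, but in the repeated-measures model for quality of life as a secondary outcome, not in the QALY regression.

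**The concern.** A QALY total built from baseline and follow-up EQ-5D depends on the baseline value in two ways. The baseline value contributes directly to the total, and it predicts the later values. Nothing in the allocation balances it. In a model without it, a chance difference between arms at screening appears in the QALY difference, and variation that the baseline value could explain stays in the residual.

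At stake is the precision of the QALY difference, which is the denominator of the incremental cost per QALY, a pre-specified secondary outcome (Protocol 3.2.2). Protocol 6.2.2 also makes the size of the QALY gain part of the condition for longer-term modelling. Leaving the covariates open would also leave an analyst's choice on this result unless the economic analysis plan closes it.

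**Working it through.** **Plan's own figure.** The documents give no SD, correlation, standard error or power for QALYs, so there is no QALY figure to reproduce. The one design calculation is the 222 primary events in Protocol 6.1. It reproduces: the Schoenfeld formula at a hazard ratio of 0.67, two-sided 5% and 85% power gives 4 × (1.960 + 1.036)² / (ln 0.67)² = 224 events, and 222 events give 84.7% power. It has no bearing on the QALY model.

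**Inputs from the documents.** EQ-5D at screening, 2 years and final assessment (Protocol 4.7); QALYs to 4 years (Protocol 6.2.2); about 530 per arm (Protocol Trial Summary).

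**Assumptions, not in the documents.** The QALY is a trapezoidal area under the curve with points at 0, 2 and 4 years; the EQ-5D SD is the same at each time; there is one common correlation r between time points, from 0.3 to 0.7; the regression is linear with an identity link. An SD of 0.25 is used for illustration only, and the ratio of standard errors does not depend on it when there are no deaths.

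**Formulas.** With B the baseline index and Y2, Y4 the follow-up values, Q = B + 2·Y2 + Y4.

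- Var(Q) = SD² × (6 + 10r)
- Cov(Q, B) = SD² × (1 + 3r), so a baseline gap d carries d × (1 + 3r) into the unadjusted QALY difference. Of this, 1.0 × d is mechanical, because baseline has one of the four years of weight.
- R² = (1 + 3r)² / (6 + 10r)
- Unadjusted SE ÷ adjusted SE = 1 / √(1 − R²)

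**No deaths.**

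| r | Carry-over of d | R² | SE ratio |
|---|---|---|---|
| 0.3 | 1.9 | 3.61 / 9 = 0.401 | 1.29 |
| 0.5 | 2.5 | 6.25 / 11 = 0.568 | 1.52 |
| 0.7 | 3.1 | 9.61 / 13 = 0.739 | 1.96 |

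**With deaths.** Death adds QALY variation that baseline EQ-5D does not explain here, so the gain from adjustment shrinks. The ratios below come from simulation with death times uniform over 4 years, unrelated to EQ-5D, with no QALYs after death, a mean index of 0.75 and SD 0.25.

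| r | 5% deaths | 10% deaths |
|---|---|---|
| 0.3 | 1.21 | 1.16 |
| 0.5 | 1.36 | 1.28 |
| 0.7 | 1.62 | 1.45 |

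**Other variations, no deaths.** Discounting at 3.5% gives 1.31, 1.54 and 1.98 at r = 0.3, 0.5 and 0.7. If correlation falls with the interval, with 0.5 between adjacent points and 0.4 between baseline and 4 years, the ratio is 1.46; with 0.7 and 0.6 it is 1.84.

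**Illustration at r = 0.5, SD 0.25, no deaths.**

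- Unadjusted SE = 0.25 × √11 × √(2/530) = 0.0509 QALYs
- Adjusted SE = 0.25 × √(11 − 6.25) × √(2/530) = 0.0335 QALYs
- One-SE chance baseline gap = 0.25 × √(2/530) = 0.0154, which moves the unadjusted QALY difference by 2.5 × 0.0154 = 0.038

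**The case against.** The strongest reply is that the protocol is silent here and has not chosen an unadjusted model. The paragraph places the whole economic analysis under a plan to be completed before unblinding, the SAP defers to the same kind of document, and that plan may already name baseline EQ-5D. What the documents do show points towards adjustment: the cost model uses baseline health status as its example, and SAP 7.1 adjusts the EQ-5D index for its own baseline. This stands. A reader might infer that the trial has decided against adjustment, but no sentence says so. The deferral does not remove the point, however, because the protocol chose to state covariates for one model and not for the other, and SAP 7.1 does not govern the QALY.

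A reader might also infer that the unadjusted QALY difference would be biased, or that a small baseline gap could decide the cost-effectiveness answer. Neither is supported. Under randomisation the unadjusted difference is unbiased and its standard error already allows for chance imbalance. The documents give no expected cost difference, QALY gain or threshold against which a shift could be called decisive. Protocol 6.2.2 also plans cost per progression averted and, under stated conditions, longer-term modelling with sensitivity analysis.

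Lastly, the loss of precision depends on figures that the documents do not contain. At the low end of the range it is modest, about 16%.

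**Conclusion.** The point holds as an omission that should be closed. Run as written, the QALY regression would be unbiased on average but would leave out a pre-randomisation covariate that is both part of the outcome and a predictor of the rest of it. On the stated assumptions (area-under-the-curve QALY at 0, 2 and 4 years, EQ-5D correlations of 0.3 to 0.7, 0 to 10% deaths) its standard error would be about 1.2 to 2.0 times the adjusted one; the computed extremes are 1.16 and 1.96. The direction is the same at every correlation tried, but the size cannot be fixed from the documents. A claim that the standard error is far larger than necessary would go beyond them.

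The primary outcome and the SAP's own EQ-5D analysis are unaffected. If the economic analysis plan already specifies the adjustment, all that remains is to align the wording of 6.2.2.

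**What to change.** Before unblinding, state in Protocol 6.2.2 and in the economic analysis plan that the QALY regression includes the screening EQ-5D index and the minimisation factors. If the plan already says so, confirm it and bring 6.2.2 into line. Name the EQ-5D index explicitly, because the cost model's wording gives baseline health status only as an example and leaves adjustment to judgement. This would match the cost model in principle and the EQ-5D model in SAP 7.1, which already takes the screening value as baseline.

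The screening questionnaire is completed before run-in drug is sent (Protocol 4.5.1 and 4.5.3), so it is a valid pre-randomisation covariate. The cost is one sentence in each document and no new data.

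### Long-term cost-effectiveness modelling is tied to one kind of 4-year result, so the time horizon depends on the data and can move in one direction only

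*Protocol*

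**What the plan says.** Protocol 6.2.2 (Economic evaluation) sets out two analyses.

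- **Within-trial analysis, unconditional.** Cost per progression averted is estimated. Mean QALY differences are also estimated, "allowing the incremental cost-per QALY to be estimated for fenofibrate versus placebo based on data collected to 4 years".
- **Extrapolated analysis, conditional.** The trigger has a cost part, "If the use of fenofibrate is found to result in an increased cost to the health service at four years", and a benefit part that describes a modest slowing of progression. The sentence then gives the rest of the trigger and the action together: "a QALY gain of insufficient size to justify the extra cost, modelling will be used to extrapolate costs and QALYs beyond the follow-up period". The method is the "fitting of parametric survival curves to the observed progression data, to predict progression beyond four years", with downstream costs and outcomes then modelled from trial and published data. The stated purpose is: "This will allow longer-term cost-effectiveness, in terms of the incremental cost per QALY gained, to be estimated for fenofibrate versus placebo". The robustness of "model based estimates of cost-effectiveness will be assessed using deterministic and probabilistic sensitivity analysis".

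The same section says the economic analysis will follow its own plan, to be finished before unblinding. SAP 4.4.3 likewise leaves the detail to a separate document. That plan is not among the documents reviewed. Protocol 3.2.2 lists total cost and cost-effectiveness as secondary outcomes, with no time horizon.

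**The concern.** Whether a longer horizon is examined is decided by the unblinded 4-year result. If fenofibrate costs more and its QALY gain falls somewhat short, the question is asked again over a longer period. If fenofibrate looks cost-effective at 4 years, nothing in the two documents asks whether that holds later, when drug cost may continue and the effect may or may not persist.

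The condition is also undefined. Neither document says how small a reduction in progression counts as modest, or what cost per QALY would be justified. Unless the separate plan fixes these, the decision to model is a judgement made with the results in view.

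SAP 4.4.3 says the economic work is meant to guide how health care providers use the drug. A reported cost per QALY whose horizon was chosen by the data is harder to interpret for that purpose.

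**Working it through.** **1. Reading check.** The plan gives no figure on this point to reproduce. The table sets possible 4-year results against what section 6.2.2 provides.

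| 4-year result for fenofibrate | 4-year estimate | Long-term model |
|---|---|---|
| No increase in cost | Yes | Not provided for |
| Higher cost, QALY gain large enough to justify it | Yes | Not provided for |
| Higher cost, modest reduction in progression, QALY gain too small | Yes | Yes |
| Higher cost, no reduction in progression or no QALY gain, or harm | Yes | Not provided for |

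Two things follow. The model is tied to one row, in which fenofibrate shows some benefit but fails on value. The 4-year estimate appears in every row.

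**2. Search for another trigger.** SAP 4.4.3 only defers to the separate plan. Protocol 4.6.5 mentions cost-effectiveness as one use of extended follow-up, without tying it to the 4-year result, but that work needs a further protocol and new approvals. Neither commits the trial to modelling after a favourable 4-year result.

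**3. Illustration of how large the effect could be.** No input here comes from the documents. Assume the 4-year and long-term net-benefit estimates are bivariate normal, each with standard error 1 and correlation ρ, and call an estimate favourable if it exceeds zero. Assume further that modelling follows every unfavourable 4-year result and that either favourable result decides the conclusion. Then

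P(favourable) = 1 − P(both estimates below zero).

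With true net benefit zero on both horizons this becomes 1 − [1/4 + arcsin(ρ)/(2π)]. For ρ = 0.5: arcsin(0.5) = 0.5236, 0.5236/6.2832 = 0.0833, and 1 − 0.3333 = 0.667.

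| True net benefit (4-year, long-term), in SE | One fixed horizon | ρ = 0.3 | ρ = 0.5 | ρ = 0.7 | ρ = 0.9 |
|---|---|---|---|---|---|
| 0, 0 | 0.50 | 0.702 | 0.667 | 0.627 | 0.572 |
| −1, −1 | 0.159 | 0.272 | 0.255 | 0.233 | 0.202 |
| 0, −1 | 0.50 (4-year) or 0.159 (long-term) | 0.550 | 0.531 | 0.513 | 0.501 |
| −1, +1 | 0.159 (4-year) or 0.841 (long-term) | 0.852 | 0.845 | 0.842 | 0.841 |

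With equal true values on both horizons, the rise over a fixed horizon runs from about 4 percentage points (0.202 − 0.159) to about 20 (0.702 − 0.50). With unequal values, the rise over the more favourable horizon is small and vanishes as the correlation grows. The third row represents an effect that wanes: the rule then behaves almost as if only the 4-year horizon existed, and the less favourable long-term answer has little influence.

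At each assumed correlation these figures are upper bounds. The protocol's trigger is narrower than any unfavourable result, and the documents do not state that either favourable result decides.

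**The case against.** The strongest reply is that the condition is sensible. The protocol's rationale describes retinopathy as slowly progressive. A preventive drug incurs its cost early and may repay it late, so a 4-year cut-off can understate its value. Extrapolation matters most where there is real but insufficient benefit at 4 years, and that is where the plan calls for it. This stands as a defence of extrapolating. It does not justify making extrapolation conditional, because a longer horizon could also be less favourable and the protocol fixes no assumption about persistence of effect. The sensitivity analyses test the model once it is run; they do not bear on the choice to run it.

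A reader might infer something stronger: that every unfavourable 4-year result gets a second attempt, that a favourable one can never be tested, and that the economic conclusion is therefore biased towards fenofibrate. The documents do not support this.

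- The trigger does not cover absence of benefit, or harm.
- The text says if, not only if. That there is no other trigger is an inference from silence, and the separate plan could supply one.
- The 4-year figure is always produced. Nothing says the modelled result replaces it or that the better of the two decides.
- The model may itself come out unfavourable.
- The direction of any net error is not established, given that the 4-year horizon may understate value.

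**Conclusion.** The concern holds as a risk, not as a demonstrated bias. On the available text, the use of a longer horizon depends on the 4-year result, runs in one direction, and rests on terms with no numeric definition. Any tilt towards fenofibrate depends on how the two results are weighed in the conclusion, which neither document states, and on whether the separate economic analysis plan leaves the condition in place.

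The size cannot be derived from the documents. The 57% to 70% range, against 50% for a single fixed horizon, is an upper-bound illustration for correlations from 0.9 down to 0.3. It assumes zero true net benefit on both horizons, modelling after every unfavourable 4-year result, and a rule that either favourable result decides. It should not be quoted as an estimate for this trial. The point affects the economic secondary outcomes only.

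**What to change.** In Protocol 6.2.2, delete the condition. State that the within-trial 4-year analysis and the extrapolated analysis will both be run and reported whatever the 4-year result. Before unblinding, fix the following in the economic analysis plan:

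- which of the two analyses is the base case;
- the time horizon of the model and the discounting;
- the cost-effectiveness threshold against which results are judged;
- the scenarios for duration of effect after 4 years, including waning.

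If the economic analysis plan already does this, say so and align section 6.2.2 with it.

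The model is already foreseen, so the cost is a short text change and some extra health-economist time in those cases where the present condition would not have been met. No new data collection is needed.

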## 7 DATA HANDLING

A web-based eCRF and dedicated TMS will be used to collect study data from the screening and randomisation visits as well as for recording subsequent follow-up assessments of participants every six months. The follow-up assessments (questionnaires) will be conducted as a telephone interview by the LCC nurse, or by review of medical records where necessary. All data in the study will be processed electronically using a set of custom-written applications. CCO staff will use a suite of administration applications to manage sites and study participants, including clinical supervision (review of reported SAEs and routinely collected blood results), management of follow-up and compliance, collection of supporting documentation for relevant events and event adjudication (where relevant). All data will be stored securely. All data accesses will require a unique username and password, and any changes to data will require the user to enter their username and password as an electronic signature. Staff will have access restricted to only the functionality and data that are appropriate to their role in the study. Possible errors or omissions in the completion of eCRFs by research staff will result either in immediate queries (e.g. if pre-set boundaries are exceeded) or subsequent data queries. Errors or omissions in the completion of forms by participants will result, if appropriate, in requests to participants for clarification. Procedures for determining if changes to recorded data are appropriate will be developed and implemented prior to unblinding of the study results. All changes to the data will result in an audit trail. The CCO is also responsible for seeking information regarding pre-specified outcomes, deaths and hospitalisations via linkage to data registries.

### 7.1 SOURCE DATA

Data recorded in the eCRF from face-to-face visits with participants, lists of potentially eligible patients provided by SDRN and known through responses to DES mail-out and HIC mail-out invitations (to be stored within respective LCCs and/or the CCO), electronically completed questionnaire data, information obtained from telephone calls to the Freephone number regarding the study, information obtained via electronic linkage to central registries regarding pre-specified outcomes and other events, and biochemistry results, pharmacy records (from the commercial partner who will package, store, select and send out study drug by routine post) and documents collected regarding medical events of interest (including copies of information regarding eye procedures) will constitute the 'source documents' for the trial. The CCO will retain these data and records for at least 25 years (identifiable data for 10 years) after the end of the trial except in the case of any documentation which is legally required to be retained in Scotland in which case such documents will be stored at the University of Glasgow under the same conditions. Regulatory Authorities will have the right, in accordance with Good Clinical Practice (GCP) guidelines, to commission a confidential audit of such records while the trial is in progress or thereafter.

### 7.2 ACCESS TO DATA

Records will be kept in a secure storage area with limited access. CTSU is a secure building with access limited to employees and authorised visitors. The study servers are located in a climate controlled secure enclosure to which only system support staff have access. Direct access will be granted to authorised representatives from the Sponsor, host institution and the regulatory authorities to permit trial-related monitoring, audits and inspections.

### **7.3 DATA PROTECTION AND PATIENT CONFIDENTIALITY**

All investigators and trial site staff will comply with the requirements of the United Kingdom General Data Protection Regulation (UK-GDPR) and Data Protection Act 2018 with regards to the collection, storage, processing and disclosure of personal information. At baseline, identifiable data will be recorded as detailed in section 4.5.1 by the LCCs. This will include the CHI number which is crucial for performing electronic linkages with relevant registries. Identifiable details will be stored in a Contact Database in encrypted format with controlled access for research staff in line with departmental security policies. Participants will be identified throughout by means of a unique participant ID number made up of an unrelated sequence of numbers. Local sites will securely store source data including ICFs, biochemistry results, and information regarding any events of interest and these documents will have identifiable data on them. Questionnaire data will be collected electronically, processed and securely stored at the CCO.

Linkage to health registries is entirely dependent on use of each participant's CHI number and data will be collected using pseudonymisation. For the purposes of data linkage, named colleagues in each registry (e.g. eDRIS, SCI Diabetes, DES) will be sent a list of CHI numbers and other identifiable data that they require for participants along with a unique trial identifier by the CCO. Data returned to the CCO will include the relevant results and/or outcomes along with the unique trial identifiers but no identifiable characteristics. The data will be incorporated into the TMS. Data transmitted for any regulatory purposes will contain no identifiable data. PBPP approval is required for linkage to Scottish health registries and this will be required prior to any linkage.

